A major assumption is that there will be high fidelity of the interventions. We will assess adherence to the interventions as a key element of fidelity (Carroll et al., 2007). Adherence will include subcategories of content, frequency, duration and dose (Carroll et al., 2007). The extent to which the intended content or frequency of WhatsApp and docu-drama are implemented will

represent the degree of implementation fidelity achieved for the two interventions (Carroll et al., 2007; Song et al., 2010).

Study Population

Inclusion Criteria

Docu-drama design

Design workshop participants will be drawn from blood donors, non-blood donors, drama experts, drama actors, and communication professionals. All must be at least 18 years old, consent to participate and understand English.

WhatsApp intervention design

Key informants will be drawn from the NBSG staff, community-based blood donation volunteers, blood donors, and non-blood donors. All must be at least 18 years old, consent to participate, and understand one of English, Twi, or Ga.

Pilot RCT

- At least 18 years-old
- First-time whole blood donor with the SZBC of the NBSG
- Eligible to donate again
- Consent to participate
- Understands one of English, Twi, or Ga
- Have a smart phone
- Have, or be willing to sign up for an active WhatsApp account

Docu-drama test-run

- At least 18 years-old
- First-time whole blood donor with the SZBC of the NBSG
- Eligible to donate again
- Consent to participate
- Understands one of English, Twi, or Ga

Exclusion Criteria

Docu-drama design

Do not meet the above inclusion criteria

WhatsApp intervention design

Do not meet the above inclusion criteria

Pilot RCT

History of more than one lifetime whole blood donation (with any blood centre)

Docu-drama test-run

History of more than one lifetime whole blood donation (with any blood centre)

Outcome measures

Primary Outcome

The primary outcome for the pilot RCT is to estimate the proportion of return blood donation attempts within six months of enrollment for each arm.

Secondary Outcomes

The secondary outcomes are the following measures.

WhatsApp and control

- Blood donation attitudes,
- subjective norms,
- perceived behavioural control,
- intention,
- ease of use of WhatsApp,
- perceived usefulness of WhatsApp.

Docu-drama, WhatsApp and control

- Intention of using the intervention

- Acceptability of the intervention
- Feasibility of the intervention
- Cultural appropriateness of the intervention

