The participants will be invited to participate in screening after blood donation at SZBC sites.

Table 1: Schedule of assessments for pilot RCT

Assessment	Screening (At first-time donation)	Baseline A pre- randomization (Day 0)	Baseline B post- randomization (Day 0)	6-month follow-up (Days 176- 190) ¹	6-12 months follow-up
Informed Consent Form	X				
Demographics	X				
Blood donation attitudes, subjective norms, perceived behavioural control, and intention		X		X	
Randomization			X		
Intention of using the intervention			X		
Acceptability of the intervention			X	X	
Feasibility of the intervention			X	X	
Cultural appropriateness of the intervention			X	X	
Perceived usefulness of the intervention			X	X	
Perceived ease of use of the intervention			X	X	
Intervention relatedness			X	X	
Return blood donation attempts ²				X	
Focus groups of participant views of acceptability, effectiveness, feasibility, and cultural appropriateness					X
Note: The participants involved in the test-run of the docu-drama will be surveyed prior-to and after the docu-drama with all instruments (except blood donation attempts) and participate in facilitator-led focus groups.					
¹ 6-months with a 2-week window.					
² Donor return will be assessed via telephone calls and cross-checked with SZBC donor records.					

Follow-up assessments for the pilot RCT

There will be two follow-up assessments.

6 months

The 6-month assessment for the pilot RCT will occur over the phone with a 2-week window of the 6-month pilot. Donor return will be assessed via telephone calls and cross-checked with SZBC donor records. The six-month follow-up will repeat baseline post-randomization questionnaires and include the intention of using the intervention, acceptability of the intervention, feasibility of the intervention, cultural appropriateness of the intervention, perceived ease of use of the intervention, perceived usefulness of the intervention, and intervention relatedness. In line with definitions of acceptability, appropriateness and feasibility given by Weiner et al. (2017), we defined these characteristics as follows:

Acceptability is the perception among first-time blood donors that an intervention is agreeable or satisfactory for promoting blood donation. Thus, acceptability will be measured with a five-item questionnaire.

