Read each statement to the participant and have them indicate True or False.

	True	False
1. I need a special invitation to donate blood.	1 	0 
2. All people with diabetes or hypertension can donate blood.	1 	0 
3. A menstruating woman can donate blood.	1 	0 
4. 'Skinny' people can donate blood.	1 	0 
5. Breastfeeding women can donate blood.	1 	0 
6. People with HIV/AIDS can donate blood.	1 	0 
7. A person with a fever on the day of donation can still donate blood.	1 	0 
8. A person with low blood level can donate blood.	1 	0 
9. A man will not become impotent for donating blood.	1 	0 
10. I can donate blood at any donation site that I choose.	1 	0 
11. My blood can only be given to my family member or friend.	1 	0 
12. My donated blood can save the life of another person.	1 	0 

B. Beliefs and Perceptions

What follows are a number of statements related to the participant's perceptions or beliefs about donating blood. Read each statement to the participant, and have them indicate where they fall on the scale from 1 (strongly disagree) to 5 (strongly agree) for each statement.

	Strongly Disagree					Strongly Agree				
1. Blood is life	1 	2 	3 	4 	5 					
2. Blood has spiritual importance	1 	2 	3 	4 	5 					
3. Blood is sacred/extraordinary	1 	2 	3 	4 	5 					
4. Donated blood is sold	1 	2 	3 	4 	5 					

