2. I feel understood by the people I know when I'm on WhatsApp	1 	2 	3 	4 	5 
3. My WhatsApp friends feel like family	1 	2 	3 	4 	5 
4. I am able to relate to my WhatsApp friends	1 	2 	3 	4 	5 
5. I find myself actively involved in WhatsApp friends' lives	1 	2 	3 	4 	5 
6. I see WhatsApp friends as friendly and approachable	1 	2 	3 	4 	5 
7. I feel like an outsider when I'm on WhatsApp	1 	2 	3 	4 	5 
8. I see myself as a loner when I am on WhatsApp	1 	2 	3 	4 	5 
9. Even around WhatsApp friends I know, I don't feel that I really belong	1 	2 	3 	4 	5 
10. I feel disconnected from the WhatsApp world around me	1 	2 	3 	4 	5 
11. I don't feel related to most people on WhatsApp	1 	2 	3 	4 	5 
12. I don't feel I participate with anyone or any group on WhatsApp	1 	2 	3 	4 	5 

Month 6

Participant ID:

Bloodsafe Logo
PlaceholderParticipant
3-letter code:

--	--	--

P. Return Blood Donation Attempts

1. Has the participant attempted to donate blood in the past six months?

0 No →

1.a Please indicate the reason why the participant did not donate blood.

- 1 No reason

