1. "I want to make sure you understand that I'm not selling or promoting anything. I'm calling in regard to the earlier request to interview you on blood donation. I was wondering if this would be a good time to go through the survey with you. It only takes about 30 minutes."
2. "I'm sorry, I realize I've called at a bad time, but we are conducting a very important study that will have a direct impact on blood donation as we informed you the last time, and I'd like to have a chance to get your opinions. When would be the best time to call you back?" (Be sure to use assertive language such as, "When can I call you back?" instead of "Can I call you back?")

I don't have time now.

"As explained to you the last time, the survey only takes about 30 minutes and I can assure you that your responses will have a direct impact on blood donation in Ghana. If now is not a good time, when would be the best time to call you back?"

I agree with the rest of the questions.

"We're very interested in your opinions on the rest of the questions because your opinion on all the questions is very important for the study."

I can no longer continue with the interview:

"We're very interested in your opinions. When can I call you?"

B. CONDUCTING THE PHONE INTERVIEW

1. Each interview will last about 30 minutes. Ask interviewer at 5 minutes intervals if they are still willing to proceed with the interview.
2. The participant must be informed about the next set of questions and whether they are willing to continue with the interview or where the subject matter changes during the interview.

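### The primary-outcome question comes last in the Month 6 phone interview, so a break-off that is never resumed loses the self-reported donation attempt

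*Combined protocol and SAP*

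**What the plan says.** - **Section on outcome measures:** the definition for the pilot reads as follows: "The primary outcome for the pilot RCT is to estimate the proportion of return blood donation attempts within six months of enrollment for each arm".
- **Follow-up assessments for the pilot RCT, 6 months:** "The 6-month assessment for the pilot RCT will occur over the phone with a 2-week window of the 6-month pilot". Table 1 gives the window as days 176 to 190.
- **Second source (same section, and Table 1 footnote 2):** "Donor return will be assessed via telephone calls and cross-checked with SZBC donor records".
- **Study Tools, item 10 (Month 6 case report form):** the form opens with section A, Knowledge. The return question, "Has the participant attempted to donate blood in the past six months", is in the final section, "P. Return Blood Donation Attempts", just above the signature line. Sub-item 1.c of that section codes why an attempt failed: screening or selection, venipuncture, waiting time, or other.
- **Study Tools, item 18 (Phone Interview Guide), part B:** "Each interview will last about 30 minutes. Ask interviewer at 5 minutes intervals if they are still willing to proceed with the interview". The second numbered instruction there adds a check of willingness when a new set of questions begins or the subject changes. Part A scripts a reply for a participant who says they cannot go on; the reply asks when to call again.
- **Quantitative Data Analysis:** multiple imputation by chained equations is to be used for missing data if necessary.

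**The concern.** The study's own tools foresee that some participants will stop part-way, and they put the primary outcome after nearly all of the points at which stopping is invited. A caller who works through the form in its printed order collects the secondary scales first and reaches the primary item at the end. Anyone who stops and is not reached again gives partial secondary data and no self-report of the primary outcome. The reasons for not returning (sub-item 1.a), which would help in designing the larger UH3 trial, come only from the interview and are lost as well.

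At stake is how complete the return proportion is. That proportion is the figure on which the sample size is built and which the pilot exists to supply for UH3.

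**Working it through.** **1. Position of the primary item (counted on the Month 6 form).** Sections run A to F and H to P, with no G: 15 sections, 14 of them before P. Items before P:

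A 12 + B 5 + C 6 + D 6 + E 5 + F 3 + H 3 + I 3 + J 4 + K 3 + L 3 + M 3 + N 9 + O 12 = **77**.

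- 1-to-5 scales (B, C, D, E, F, L, M, N, O): 5+6+6+5+3+3+3+9+12 = 52
- True/False (A): 12
- Yes/No/I don't know (H, I, J, K): 3+3+4+3 = 13

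**2. Exit points.** In a 30-minute call, five-minute checks fall at 5, 10, 15, 20 and 25 minutes, so there are five, plus those at changes of subject.

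**3. The plan's own figures (Pilot RCT sample size).** The 80% Clopper-Pearson width at n = 59 and p = 0.20, taken from beta quantiles with x = 0.2n, is 0.1490; the plan states 0.149. Two-sided Fisher power for 3% versus 20.21% at n = 59 per arm is 0.7998; the plan states 80%. Both reproduce.

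**4. Base for the sensitivity check.** With 64 enrolled and 10% lost, 64 × 0.9 = 57.6, rounded to 58 per arm. That is already one below 59, because 59/0.9 = 65.6. This shortfall has nothing to do with question order, but it means there is no slack.

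**5. Effect of break-off.** The documents give no break-off rate and no recovery rate. Both are assumptions here:

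n = 57.6 × [1 − b × (1 − r)], with b = share of calls broken off and r = share of those recovered by call-back or records.

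| b | r | n per arm | 80% CI width at 20% |
|---|---|---|---|
| 0 | – | 58 | 0.150 |
| 5% | 0 | 57.6 × 0.95 = 54.7 → 55 | 0.155 |
| 10% | 0 | 57.6 × 0.90 = 51.8 → 52 | 0.160 |
| 5% | 0.5 | 57.6 × 0.975 = 56.2 → 56 | 0.153 |
| 10% | 0.5 | 57.6 × 0.95 = 54.7 → 55 | 0.155 |
| any | 1 | 58 | 0.150 |

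Fisher power for 3% versus 20.21% is 0.79 at n = 58, 0.76 at 55 and 0.72 at 52.

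**6. What the second source covers.** The outcome is an attempt, and sub-item 1.c shows that failed attempts count. Nothing in the plan says that SZBC records hold a deferral at screening or a donor who left because of the wait. The Study Location section says that some facilities in the catchment collect their own blood; nothing says SZBC records cover attempts there. The records are described as a cross-check, and no rule lets them set the outcome when the telephone answer is missing.

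**The case against.** The strongest reply is that a broken-off call is not a lost endpoint. Participants are first-time SZBC donors, so a successful return to SZBC can be found in the records without a finished interview. The guide meets hang-ups, lack of time and inability to continue with a call-back. This stands. A reader might infer from the layout that every break-off loses the primary outcome; the documents do not support that. What remains is that a call-back needs a second contact, within a two-week window, with someone who has already stopped once, and that the records are only a partial backstop.

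Two links are inferred. The Phone Interview Guide does not name the Month 6 visit; its use there follows from the telephone mode and from its script, which speaks of going through a survey. The form prints an order but does not make it mandatory, and section P is worded in the third person with no instruction to read it aloud, so staff could complete it separately. Both points are fair. Even so, nothing in the guide tells callers to secure section P first, and the printed order is the natural one to follow.

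The remedy also has a cost. Asking whether and why a person did not return, just before the attitude, control and intention items, could influence those answers, and they are secondary outcomes. That is a real but limited price: Baseline A already opens with a question about the donation itself.

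**Conclusion.** The point holds as a cheap improvement. Section P is last, after 77 items, in a telephone interview with repeated exit offers, and an unresumed break-off loses the self-reported attempt. Existing safeguards recover some of these, by an amount the plan does not let one calculate. Under assumed break-off of 5% or 10%, the evaluable number falls from 58 per arm to 55 or 52 with no recovery, to 56 or 55 with half recovered, and not at all with full recovery.

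Three stronger readings should be left aside.

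- **A loss of 5 to 14%.** A reader might assume that 1%, 2% or 3% stop at each of five checks and obtain 1 − (1 − h)^5 = 4.9%, 9.6% or 14.1%. Those rates are not in the documents, and the formula assumes that nothing is recovered.
- **An upward bias in the return proportion.** It is plausible that people who stop early are also less likely to have returned, and standard multiple imputation, which assumes data missing at random, would not by itself remove such a bias. But the plan does not show the link. If records were used to fill the gaps, missed failed or non-SZBC attempts would push the estimate down instead.
- **Differential loss by arm.** Sections H to M and O hold 3+3+4+3+3+3+12 = 31 items about WhatsApp, with no printed skip for controls. More break-off in the control arm is conceivable, but nothing in the documents establishes it.

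**What to change.** Move section P to the start of the Month 6 case report form, directly after identity is confirmed. Add to the Phone Interview Guide that section P is completed before the first willingness check, and that a participant who cannot do the full interview is asked section P alone.

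The cost is reordering one form and adding a short instruction to one guide. The downside is a possible small order effect on the secondary attitude, control and intention scales, which is acceptable in exchange for protecting the primary outcome.

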4.2. Enter and double-check the participant ID (PID)

4.2.1. Using the bar-code scanner, click on the blank box for entering the PID on the website randomization app, scan the PID label on the participant's folder. The PID will automatically fill in the PID number into the website randomization application.

BLOODSAFE: Standard Operating Procedure

Randomizing participants into study groups for the pilot RCT of WhatsApp and control	Version 0.3 15 Feb 2021
---	------------------------------------

4.2.2. Double-check that the scanned PID matches the pre-printed PID number located at the top of Baseline B CRF (Form C-CAD-BASB) (see Figure 2).

BLOODSAFE

Welcome [contact] Log Out

C-CAD randomization

Enter the participant's PID, select the participant's donor type, and submit for randomization.

PID: 1111-nnn-n (hyphens are optional here)

Donor type:

- Voluntary non-remunerated donor
- Family/replacement donor

Submit

Baseline B

Participant ID: (Circled)

Form Date: (Circled) Example: 01-APR-2021

Day	Month	202	Year
-----	-------	-----	------

Participant 3-letter code: Site: (Circled)

01 = Static Unit
02 = Mobile Unit

Complete this form immediately after randomization for all participants enrolled in the RCT of the C-CAD study.

A. Randomization

- Date of participant randomization: (Circled) Example: 01-APR-2021
- Indicate which arm of the study the participant is in. Follow the instructions listed for the arm.

1 Control
2 WhatsApp

Figure 2: Double-check that the scanned PID matches the pre-printed PID number on the Baseline B CRF.

4.3. Enter the Donor type as defined by the C-CAD study definitions and submit the website randomization application (see Figure 3).

BLOODSAFE

Welcome [contact] Log Out

C-CAD randomization

Enter the participant's PID, select the participant's donor type, and submit for randomization.

PID: 1111-nnn-n (hyphens are optional here)

Donor type:

- Voluntary non-remunerated donor
- Family/replacement donor

Submit (Circled)

Figure 3: Enter Donor type and Submit.

4.4. The C-CAD Randomization application will display the random group allocation outcome (see Figure 4).

BLOODSAFE: Standard Operating Procedure

Randomizing participants into study groups for the pilot RCT of WhatsApp and control	Version 0.3 15 Feb 2021
--	----------------------------

Research Projects in

- Ghana
- Kenya
- Malawi

News

Research Projects in

- Ghana
- Kenya
- Malawi

C-CAD randomization assignment

The participant with PID **9111-012-2** has been randomized to the **WhatsApp** arm of the study.

[Randomize another PID](#)

C-CAD randomization assignment

The participant with PID **9111-013-0** has been randomized to the **Control** arm of the study.

[Randomize another PID](#)

Figure 4: Example of randomization application outcomes screen for two different PIDs.

4.5. Record the date, randomization stratum, and outcome of the randomization outcome on the Baseline B CRF (C-CAD BASB) Section A. Randomization (see Figure 5).

Baseline B

Participant ID:
	
Form Date: (example: 01-APR-2021)
 
 
 Day	Month	2	0	2	Year	
 
	Day	Month	2	0	2	Year	
Participant 3-letter code:

Day	Month	2	0	2	Year			
								

Complete this form immediately after the Baseline A form for all participants enrolled in the pilot RCT of WhatsApp and Control.

A. Randomization

1. Date of participant randomization:

Day	Month	2	0	2	Year
-----	-------	---	---	---	------
2. Indicate which randomization stratum the participant is in
 - Voluntary non-remunerated blood donor
 - Family/replacement donor
3. Indicate which arm of the study the participant is in.
 - Control
 - WhatsApp

Figure 5: Complete Section A. Randomization with the date, stratum and randomization application outcome.

18. Phone Interview Guide

Title: Community-based communication interventions for increasing the blood donor pool in Ghana: a randomized controlled trial

Phone Interview Guide

Introduction should be brief, clearly identifying the caller, caller's institution and referring to the invitation to participation. In asking to speak with the intended participant, the actual nature of the call should not be disclosed to a third party. For instance, it is enough to say "*I would like to speak with... in relation to having scheduled a phone interview earlier about blood donation*".

A. STRATEGIES FOR INCREASING PHONE INTERVIEW PARTICIPATION

Hangs up before hearing reason for survey. Call back!

1. "I want to make sure you understand that I'm not selling or promoting anything. I'm calling in regard to the earlier request to interview you on blood donation. I was wondering if this would be a good time to go through the survey with you. It only takes about 30 minutes."
2. "I'm sorry, I realize I've called at a bad time, but we are conducting a very important study that will have a direct impact on blood donation as we informed you the last time, and I'd like to have a chance to get your opinions. When would be the best time to call you back?" (Be sure to use assertive language such as, "When can I call you back?" instead of "Can I call you back?")

I don't have time now.

"As explained to you the last time, the survey only takes about 30 minutes and I can assure you that your responses will have a direct impact on blood donation in Ghana. If now is not a good time, when would be the best time to call you back?"

I agree with the rest of the questions.

"We're very interested in your opinions on the rest of the questions because your opinion on all the questions is very important for the study."

I can no longer continue with the interview:

"We're very interested in your opinions. When can I call you?"

B. CONDUCTING THE PHONE INTERVIEW

1. Each interview will last about 30 minutes. Ask interviewer at 5 minutes intervals if they are still willing to proceed with the interview.
2. The participant must be informed about the next set of questions and whether they are willing to continue with the interview or where the subject matter changes during the interview.
